Hypoglycaemia in subjects suffering from type 2 diabetes may have substantial consequences including a significant negative impact on quality of life [1], [2]. Further, repeated minor hypoglycaemias may result in significant productivity losses. In healthy subjects a number of studies show that during a hypoglycaemic episode with plasma levels of 2.2 – 2.5 mmol/L (40-45 mg/dl) brain areas responsible for cognition have an altered neuronal function when measuring cerebral blood flow [3], [4]. This is accompanied by severely impaired cognitive function with a reduced ability to solve simple cognitive tasks. At higher levels of glucose (above 3 mmol/L (54 mg/dl)), it remains to be settled whether cognitive functions are also affected negatively and whether this may be accompanied by changes in brain metabolism. Apart from raising the blood glucose directly or indirectly via glucagon, no treatment for hypoglycaemia exists, but since GLP-1 based therapies used in type 2 diabetes may affect brain glucose consumption, therapeutic interventions to prevent negative results of hypoglycaemia may eventually become clinically possible [5].

Here, we propose to provide quantitative results on cognition during an acute mild hypoglycaemic episode (target plasma glucose 3 mmol/L). Data will be provided on executive function, attention and memory.

Objectives and endpoints

Objective

To investigate our hypothesis that acute mild hypoglycaemia in patients with diabetes type 2 volunteers is associated with cognitive impairment of executive function, attention and memory.

Primary endpoint

- Performance on the Symbol Digit Modalities Test (SDMT)

Secondary endpoints

- Additional measures of executive function, attention and memory (see section on neurocognitive tests).

Hypothesis

- Mild hypoglycaemia attenuates cognitive performance in type 2 diabetes.

[figure not shown]
Study design

Our study is a randomised, single-centre, single-blinded, two-period cross-over trial in subjects with type 2 diabetes examining the effect of an acute hypoglycaemic episode on cognitive function.

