Each subject undergoes two experimental days in randomized order with a 21-42 day interval, Day A and Day B. At each visit they will undergo a clamp procedure where their plasma glucose levels will be clamped at either a hypoglycaemic (PG < 3.1 mmol/L, goal during clamp 2,8-3,2) or at an euglycaemic level (6 mmol/L, goal during clamp 5,8- 6,2). During the two conditions (hypoglycaemia or euglycaemia) cognitive performance will be assessed by validated cognitive tests.

The trial consists of a screening visit (Day 0) 2-35 days prior to two following experimental visits (Day A and B), that will be separated by a period of 21-42 days during which the participants will resume their normal medical and lifestyle treatments.

An information visit prior the screening visit and a phone call follow-up after completion of the second experimental day are included in the trial as well.

Participants

Participant Selection

Number of participants: Based on previous studies and the following power calculation, we estimate that a study will be informative with 28 participants.

Inclusion criteria:

- Informed and written consent
- Clinically diagnosed type 2 diabetes mellitus for at least 3 months (diagnosed according to the criteria of the World Health Organization (WHO)).
- Normal haemoglobin ≥ 8.0 mmol/L (male) or ≥ 6.4 mmol/L (female)
- Male or female participants aged 35-70 years, both inclusive.
- Treated with diet or any antidiabetic medication except sulfonylureas, meglitinides or insulin.
- HbA1c ≤ 9.0 % by local laboratory analysis.
- BMI >23 kg/m² and <35 kg/m²

Exclusion criteria:

- Receipt of any investigational medicinal product within 3 months before screening in this trial.
- Liver disease (alanine aminotransferase (ALAT) and/or serum aspartate aminotransferase (ASAT) >2 times normal values) or history of hepatobiliary disorder.
- Nephropathy (serum creatinine levels ≥ 126 $\mu\text{mol/L}$ (male) or ≥ 111 $\mu\text{mol/L}$ (female)).
- Cardiac problems defined as decompensated heart failure (New York Heart Association (NYHA) class III and IV) at any time and/or angina pectoris within the last 12 months and/or acute myocardial infarction at any time.
- Active or recent malignant disease.
- Treatment with drugs that cannot be paused for 12 hours.
- Repeated resting blood pressure at screening outside the range 90–140 mmHg for systolic or 50–90 mmHg for diastolic. This exclusion criterion also pertains to subjects taking antihypertensives.

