On the first experimental day a hyperinsulinaemic hypoglycemic clamp is performed. At time 0 minutes, insulin infusion is initiated (Actrapid, Novo Nordisk). Plasma glucose is measured bedside every 5 minutes, allowing the plasma glucose level to be clamped on 3 mmol/L using an adjustable continuous infusion of 20 % glucose. Neurocognitive testing is initiated when glucose levels have been stabilized for 40 minutes and lasts for approximately 45 minutes.

Day B

Hyperinsulinaemic hyperglycemic clamp. Equal to Day A except that the plasma glucose level is clamped on 6 mmol/L.

Blood specimens:

Blood will be drawn at 30 after goal PG is reached, into chilled tubes containing heparin for analyses of insulin, C-peptide, epinephrine, glucagon, cortisol and growth hormone. Plasma samples are stored at -20°C until analysis. For bedside measurements of plasma glucose, blood is added to fluoride tubes and centrifuged at room temperature immediately for 30 seconds at 7400g.

Analytical procedures:

Plasma glucose concentrations are measured by the glucose oxidase method. Plasma insulin and C-peptide concentrations are measured using a two-sided electrochemiluminescence immunoassay (Roche/Hitachi Modular Analytics; Roche Diagnostic GmbH).

Performance of Cognitive Tests:

Neurocognitive test battery:

The test battery includes the following neurocognitive tests: Rey Auditory Verbal Learning Test (RAVLT) [6] (verbal memory), Trail Making Test (TMT) [7] part A and B (psychomotor speed and executive function), Symbol Digit Modalities Test (SDMT) [8] (psychomotor speed and executive function), WAIS-III Letter-Number Sequencing test [9] (executive function), verbal fluency test (letters S and D) (executive function) and Rapid Visual Processing (RVP) test from the Cambridge Neuropsychological Test Automated Battery (CANTAB) (sustained attention) [10], [11]. To avoid learning effects from baseline to follow-up testing, we will use alternate versions of the tests that are associated with greatest learning effects (incl. the RAVLT). Verbal IQ is estimated with the Danish Adult Reading Test (DART) (equivalent to the National Adult Reading Test; NART). The total duration of neuropsychological testing on each occasion is approximately 45 min.

All experiments are carried out at the Department of Endocrinology, Bispebjerg University Hospital, [name], where the necessary equipment is available.

Randomisation procedure

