The participants of this randomised single-blinded study will be treated in a randomized sequence; either hypoglycaemia followed by euglycaemia or euglycaemia followed by hypoglycaemia. The investigator will be blinded to the treatment sequence until randomisation of the participant.

Calculations and statistics

Data is processed and presented with the use of standard descriptive statistics. AUCs are calculated by use of the trapezoid rule. Repeated measurement analysis of variance is used for statistical analysis of repeated measurements in the same subject. Data that is not normally distributed is compared using the Mann-Whitney U-test.

A recent trial applying the cognitive DSST score (part of the above neurocognitive test battery) in type 1 diabetes revealed a standard deviation (*SD*) between eu- and hypoglycaemia of 9 [12]. We suggest a similar level of variance in this study and from previous trial opt to detect differences of 6 or more. *P* values ≤ 0.05 will be considered as statistically significant, i.e. significance level of 5%, which will allow a sample size of 28 to yield a more than 90% high chance of detecting a true difference in cognition.

Only data from trial participants who have completed the entire study will be included in the statistical analysis.

Side effects, risks and disadvantages for participants

The 10 hour fast prior to each research day is a part of the natural nocturnal fast (10 PM - 8 AM), and is neither associated with discomfort or danger.

Insulin when administered can lead to hypoglycaemic episodes. This will sometimes appear as certain symptoms like palpitations (increased heartbeat/pulse), hunger, tremor (slight shaking), pallor, nausea, headache, sudden perspiration, feelings of anxiety, visual and speech disorders, paraesthesia (tingling and numbness in the feet and hands), symptoms of paralysis, and unsteadiness. If the condition progresses to severe hypoglycaemia, it can lead to loss of self-control, unconsciousness and, in extreme cases, death.

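### The order of the clamps is randomised and practice effects are anticipated, but no period term is specified for the primary SDMT comparison

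*Combined protocol and SAP*

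**What the plan says.** - **Design.** The Study design section states: "Our study is a randomised, single-centre, single-blinded, two-period cross-over trial in subjects with type 2 diabetes". It adds: "Each subject undergoes two experimental days in randomized order with a 21-42 day interval, Day A and Day B". The Randomisation procedure section gives the two sequences as "either hypoglycaemia followed by euglycaemia or euglycaemia followed by hypoglycaemia". The allocation method and ratio are not stated.
- **Order, elsewhere.** The Day A section reads differently: "On the first experimental day a hyperinsulinaemic hypoglycemic clamp is performed". Under Screening visit (Day 0), the first experimental day is also labelled Day A.
- **Learning.** Under Performance of Cognitive Tests, the plan says that to avoid learning effects "we will use alternate versions of the tests that are associated with greatest learning effects (incl. the RAVLT". The RAVLT is the only test named; the SDMT is neither named nor ruled out.
- **Analysis.** Calculations and statistics contains the sentence "Repeated measurement analysis of variance is used for statistical analysis of repeated measurements in the same subject". It is not tied to the SDMT and names no condition, period or sequence term. Non-normal data go to the Mann-Whitney U-test, and only participants who complete the whole study are analysed.
- **Sample size.** The same section takes an SD of 9 from a type 1 diabetes study, a difference of 6, a 5% level and 28 participants, and claims power above 90%.

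**The concern.** In a two-period cross-over each person contributes one difference between conditions. If people score higher at the second visit through practice, that gain inflates the apparent harm of hypoglycaemia in those who had hypoglycaemia first and masks it in those who had euglycaemia first. A model with a period term removes the gain. A paired comparison leaves it in the error. With equal sequences the estimate remains unbiased and the test is conservative, but the confidence interval is wider than it need be and power is lost. With unequal sequences the estimate itself moves, in a direction set by which sequence is larger. Nothing in the plan secures equal numbers among completers.

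Leaving the term open also means that whether to adjust the primary endpoint for period could be decided after the data are seen.

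The Day A wording raises a linked problem. If hypoglycaemia always came first, period and condition would coincide and no model could separate them. The whole practice gain would then count as an effect of hypoglycaemia.

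**Working it through.** **Inputs from the protocol (Calculations and statistics):** N = 28, difference δ = 6, SD = 9, level 5%.

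**Assumptions:** two-sided test; SD 9 is the SD of the within-person differences within a sequence; practice gain π at visit 2, whose size the documents do not give. The main range is 3 to 6 points, with 0 and 2 shown for comparison.

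**1. Reproduce the stated power.** SE = 9/√28 = 1.70 and δ/SE = 3.53. The non-central t with 27 df gives 92.5%; the normal approximation Φ(3.53 − 1.96) gives 94.2%. Both agree with the claim of more than 90%. Treating the conditions as independent groups gives 42% (14 per group) or 70% (28 per group), so the claim rests on a paired comparison with no period effect.

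**2. Where practice enters.** Let d = euglycaemia minus hypoglycaemia. Its mean is δ + π when hypoglycaemia is first (n₁ people) and δ − π when euglycaemia is first (n₂ people).
- Unadjusted mean of d: δ + π(n₁ − n₂)/N.
- Expected variance of d at 14/14: 81 + (28/27)π². For π = 4 this is 81 + 16.6 = 97.6, so the SD is 9.88 and the SE is 9.88/9 = 1.098 times too large.

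**3. Period-adjusted estimate.** Take the average of the two sequence means, with SE = (9/2)√(1/n₁ + 1/n₂) and 26 df. At 14/14 the SE is 1.70 and power is 92.4% whatever π is.

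**4. Equal sequences (14/14), no period term:**

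| Gain π | SD of d | SE ratio | Power | Type I error |
|---|---|---|---|---|
| 0 | 9.00 | 1.00 | 92.5% | 5.0% |
| 2 | 9.23 | 1.03 | 92% | about 4.4% |
| 3 | 9.50 | 1.06 | 91% | 3.9% |
| 4 | 9.88 | 1.10 | 89% | 3.2% |
| 5 | 10.34 | 1.15 | 87% | 2.5% |
| 6 | 10.88 | 1.21 | 85% | 1.9% |

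Power falls to 90% at a gain of about 3.5 points.

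**5. Unequal sequences, π = 4.** The first unadjusted power is with more people hypoglycaemia-first, the second with more euglycaemia-first.

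| Split | Shift = 4(n₁ − n₂)/28 | Unadjusted power | Unadjusted type I error | Adjusted power |
|---|---|---|---|---|
| 15/13 | 0.29 | 92% or 86% | 3.5% | 92.3% |
| 16/12 | 0.57 | 94% or 82% | 4.2% | 91.9% |
| 18/10 | 1.14 | 97% or 73% | about 7% | 90.2% |

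The 16/12 shift is 0.57/1.70, about a third of an SE. If allocation were unrestricted 1:1, the binomial distribution with 28 trials gives 15% for exactly 14/14, 57% for 16/12 or worse, and 18% for 18/10 or worse.

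**6. Other reading of SD 9.** If 9 already contains period variation with π = 4, the within-sequence SD is √(81 − 16) = 8.06. Power is then 94% without the period term and 97% with it.

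**7. Fixed order, hypoglycaemia first, no true effect.** The paired test is centred on π with SE 1.70 and 27 df. It rejects 40% of the time at π = 3 and 62% at π = 4.

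**The case against.** The strongest reply is that the plan contains no error here. Repeated-measures ANOVA can carry a period factor, and the section lists no model terms at all, so the missing period term is one part of a broader lack of detail. That is fair as description, but it leaves the primary analysis open on a choice that can change the result.

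The size of the problem also depends on a practice gain that the documents do not supply. The alternate test versions and the 21-42 day interval may keep it small, and the SDMT may be among the tests with alternate versions. At 3 points or less with equal sequences, the power claim survives. The SD of 9 may already include period variation, in which case the stated power is not eroded. These points stand, and every figure above is conditional on them.

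On validity, the unadjusted test is conservative at 14/14 and still below 5% type I error at 16/12. Averaged over unrestricted 1:1 allocation, its type I error is about 5% and the estimate is unbiased. This too stands. The harm is mainly lost precision, with average power about 87% at a 4-point gain, plus a shift that depends on the split that occurs. Type I error exceeds 5% only from about 17/11 (5.4% at a 4-point gain).

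Finally, the fixed-order figures belong to the conflict over clamp order, not to the missing period term. They are given only to show why that conflict must be settled, and the recommendation on the period term does not rest on them.

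**Conclusion.** The concern holds. The design randomises order, the plan anticipates learning, and no period term is specified for the primary contrast. The stated power reproduces and the sample size need not change.

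With N = 28, a 6-point difference, SD 9 within sequence and an assumed gain of 3 to 6 points, leaving out period at 14/14 lowers power from 92.4% to between 91% and 85% and makes the SE about 6% to 21% too large. With unequal sequences the estimate is also shifted, by 0.57 points at 16/12 with a 4-point gain. If no practice gain remains, nothing is lost by omitting the term, and including it costs 0.1 percentage points of power at 14/14. The plan should be changed because the gain is real under plausible conditions and the cost is negligible. The size of the benefit is uncertain.

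**What to change.** 1. **Pre-specify the model.** In Calculations and statistics, define the primary SDMT analysis as the difference between hypoglycaemia and euglycaemia from a linear model with participant, condition and period (visit 1 or 2). Comparing the period differences between the two sequences is equivalent. Report the difference with a 95% CI, and use the same model for the secondary cognitive tests. This changes only wording and costs one degree of freedom (power 92.5% to 92.4%). The visit order and assigned sequence that it needs are part of running the trial.
2. **Align the fallback.** If a rank-based alternative is kept, apply it to within-person period differences compared between sequences, so that it respects both pairing and period.
3. **Reconcile the order of the clamps.** Make Study design, Screening visit (Day 0), Day A, Day B and Randomisation procedure agree. This is a text correction, but the period adjustment depends on order varying between participants.
4. **Optional.** Use blocked allocation to keep the sequences close to equal, and balance SDMT forms across sequences. These change the randomisation list and test preparation.

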The screening visit will take place 2-35 days prior to the first experimental day (Day A). The signed and dated informed consent is assessed and inclusion and exclusion criteria are checked. Demography (date of birth, ethnicity, sex) is assessed along with current medication and medical history are recorded. Height, weight, body mass index (BMI) and blood samples (creatinine, electrolytes (Na⁺, K⁺, Ca), ALAT/ASAT, alkaline phosphatase, albumin, bilirubin, haemoglobin, plasma glucose, C-reactive protein (CRP), HbA_{1c}, coagulation tests (INR and coagulation factor II, VII and X). Date of the diabetes diagnosis and current diabetes treatment is obtained, and finally a physical examination is performed and vital signs and an ECG will be assessed.

On the basis of the screening results, eligible participants are included in the study, and dates for the two experimental days are planned.

Experimental days (Day A and B)

If a participant meets one or more of the following exclusion criteria on any of the experimental days (Day A and B), he or she will be excluded from the visit or withdrawn from the trial:

Exclusion criteria:

- Consumption of alcohol within 24 hours prior to an experimental day.
- Extensive physical exercise within 24 hours prior to an experimental visit that will interfere with trial results, as judged by the investigator.
- Any use of systemic drugs that may interfere with glucose metabolism.
- Hypoglycaemia (detected as a plasma glucose (PG) ≤ 3.9 mmol/L) within 48 hours prior to an experimental day.

Participants will be instructed to maintain a regular diet and avoid alcohol and excessive eating for 3 days before each experimental day.

Day A

Subjects arrive at the laboratory after an overnight (10 hours) fast (water, coffee, tobacco, medicine) having avoided strenuous physical activity from the day before. They are placed in a recumbent position and will have a cannula inserted into a cubital vein. Another cannula is inserted into a contralateral cubital vein for insulin and glucose infusions.

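### The only fallback named for non-normal data, the Mann-Whitney U-test, is for independent samples and discards the cross-over pairing, so a true impairment can be missed

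*Combined protocol and SAP*

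**What the plan says.** Under Study design, the trial is a "two-period cross-over trial in subjects with type 2 diabetes", and "Each subject undergoes two experimental days in randomized order with a 21-42 day interval, Day A and Day B". Under Calculations and statistics:

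- The parametric method respects the pairing: "Repeated measurement analysis of variance is used for statistical analysis of repeated measurements in the same subject".
- The fallback is: "Data that is not normally distributed is compared using the Mann-Whitney U-test".
- The analysis set is restricted: "Only data from trial participants who have completed the entire study will be included in the statistical analysis". Everyone analysed therefore has both scores.
- The sample size rests on an SD "between eu- and hypoglycaemia of 9" and a difference of 6, "which will allow a sample size of 28 to yield a more than 90% high chance of detecting a true difference in cognition".

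No signed-rank or other paired rank test is named anywhere. The plan does not describe a rank-sum test of period differences between the two sequences. It gives no criterion for non-normality and does not say whether raw scores or within-subject differences are to be examined.

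**The concern.** The Mann-Whitney test takes its null variance from two independent samples. Here the two samples are the same people tested twice. The parametric analysis keeps the pairing and the fallback drops it, so a departure from normality would also change the design that the analysis assumes.

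The fallback is not limited to any endpoint. It could reach the primary SDMT score, the secondary cognitive tests and the hormone measurements taken at both clamps. The stated power belongs to a paired comparison and does not carry over to this test. The trial has a single hypothesis, that mild hypoglycaemia impairs cognition, and the error works against detecting it.

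**Working it through.** **Inputs from the plan (Calculations and statistics).** n = 28, difference 6, SD 9, significance level 5%. Two-sided testing is assumed because the plan does not state sidedness.

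**1. The plan's own power figure.** Read 9 as the SD of the within-subject difference.

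- Noncentrality = (6/9) × √28 = 3.53, with 27 df.
- Power = 92.5%, which agrees with the stated figure of more than 90%.
- Read instead as the SD within each of two independent groups of 28, noncentrality = 6 / (9 × √(2/28)) = 2.49 with 54 df, and power = 68.8%.

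The plan's figure is therefore a paired one. The 68.8% shows only that. It is a t-test figure for uncorrelated normal scores and does not estimate the fallback's power here.

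**2. Why ignoring the pairing costs power.** With per-condition SD s and correlation ρ, the variance of the mean difference is 2s²(1−ρ)/n. A test that assumes independence uses 2s²/n. For a comparison of means, the standard error is then too large by a factor 1/√(1−ρ): 1.41 at ρ = 0.5, 1.83 at 0.7 and 2.24 at 0.8. The rank-sum test behaves in a similar way.

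**3. Simulation.** Each score is a subject component plus an independent error. Settings: n = 28, difference 6, no period effect, 20,000 trials per cell, fallback applied in every trial. Correlation and shape are assumptions.

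*(a) 9 is the SD of differences*, so s = 9/√(2(1−ρ)):

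| ρ | 0 | 0.3 | 0.5 | 0.7 | 0.8 | Signed-rank |
|---|---|---|---|---|---|---|
| s | 6.4 | 7.6 | 9.0 | 11.6 | 14.2 | |
| Mann-Whitney, skewed (exponential) | 98.8% | 94.4% | 87.7% | 70.0% | 49.9% | 95% |
| Mann-Whitney, heavy-tailed (t, 3 df) | 99.3% | 96.9% | 91.4% | 73.7% | 52.2% | 98% |
| Mann-Whitney, lognormal, log-SD 0.5 | 97.8% | 92.4% | 83.8% | 61.1% | 38.8% | 95% |
| Mann-Whitney, lognormal, log-SD 1 | 100% | 99.8% | 99.1% | 95.8% | 90.2% | 99% |

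For the first two shapes the loss is none at 0, about 1 point at 0.3, 6–7 at 0.5, 24–25 at 0.7 and about 45 at 0.8. The mild lognormal loses 11, 34 and 56 points at 0.5, 0.7 and 0.8. The strong lognormal loses 0, 3 and 9.

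*(b) 9 is the SD within each condition* (Mann-Whitney v signed-rank):

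| ρ | 0 | 0.3 | 0.5 | 0.7 | 0.8 |
|---|---|---|---|---|---|
| Skewed | 89.9 v 77.4% | 85.6 v 88.1% | 88.0 v 95.5% | 92.2 v 99.4% | 95.2 v 99.9% |
| Heavy-tailed | 90.0 v 82.7% | 89.2 v 92.2% | 91.4 v 97.6% | 94.7 v 99.8% | 96.9 v 100% |
| Lognormal, log-SD 0.5 | 83.9 v 74.9% | 81.9 v 87.3% | 83.6 v 94.5% | 88.3 v 99.4% | 92.5 v 100% |

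The largest loss is about 8 points for the first two shapes, 11 for the mild lognormal and under 1 for the strong lognormal.

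**4. Type I error (skewed and heavy-tailed).** Mann-Whitney: 0.8–0.9% at ρ = 0.5 and below 0.3% at 0.7–0.8. Signed-rank: 4.5–5.0%.

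**5. Fallback used only when a 5% Shapiro-Wilk test rejects, otherwise a paired t-test.** Reading (a), ρ = 0.5/0.7/0.8, 4,000 trials per cell. Overall power:

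| Shape, what is screened | Mann-Whitney fallback | Signed-rank fallback |
|---|---|---|
| Skewed, raw scores | 88/72/55% | 95/95/95% |
| Skewed, differences | 91/85/78% | 94/94/94% |
| Heavy-tailed, raw scores | 94/86/76% | 96/97/96% |
| Heavy-tailed, differences | 94/89/82% | 96/97/98% |
| Normal, raw scores | 90/88/86% | 92/92/93% |
| Normal, differences | 91/90/89% | 92/92/93% |

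For normal scores the fallback is triggered in only 5–10% of trials, and the overall loss, taken before rounding, is 1 to 6 points.

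**The case against.** The strongest reply concerns size. The documents give neither correlation nor shape, and the loss runs from nothing to 56 points. At correlation 0 the Mann-Whitney test does better than the signed-rank test. The large losses need reading (a), a high correlation and a fallback that always fires. Holding the difference SD at 9 pushes the per-condition SD up to 14.2 at correlation 0.8, and this drives the largest losses. When differences are screened first, the loss for skewed scores is 3, 9 and 16 points at 0.5, 0.7 and 0.8. Nothing in the plan suggests that SDMT will be non-normal. All of this stands. It limits the size and does not make the test suitable for paired scores.

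A rank-sum test also has a valid use in a two-sequence cross-over, on period differences between sequences. The plan mentions neither period differences nor a comparison of sequences, so this reading has no support in the text.

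The signed-rank test has limits of its own. It makes no allowance for period, although the cognitive-test section recognises learning effects and promises alternate versions only for the tests most affected. The simulated differences are symmetric by construction, and the 4.5–5.0% type I error depends on that. With exponential-shaped differences of mean zero and n = 28, the signed-rank test rejects in about 15% of trials, because it does not test the mean. These points bear on how the replacement is specified. They do not rescue the stated fallback.

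**Conclusion.** The concern holds. The named fallback is the wrong test for this design as written, and this is more than a missing detail. The sample size is not at fault: 28 participants give 92.5% power for a paired analysis with a difference SD of 9.

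The consequence is conditional. It arises only for outcomes judged non-normal, and its size depends on an unknown positive correlation, on shape and on which SD the 9 represents. At a correlation of 0.5 the loss for skewed or heavy-tailed scores is roughly 6 to 8 points under either reading. At higher correlations it grows steeply under reading (a) and stays modest under reading (b). With positive correlation the error is conservative, so a false claim of impairment is not the worry. This should be corrected before analysis.

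**What to change.** Replace the fallback sentence in Calculations and statistics with:

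> Normality is judged on the within-subject differences (model residuals), not on the raw scores. If it is violated, the two conditions are compared with a Wilcoxon signed-rank test on the within-subject differences, reported with the Hodges-Lehmann estimate and 95% CI.

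State in advance the criterion for violation.

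If the main analysis includes a period term, a rank-sum test of period differences between the two randomised sequence groups is an acceptable alternative that also allows for period. Before any sequence-based test is specified, two parts of the protocol must be reconciled: the Screening visit and Day A sections place the hypoglycaemic clamp on the first experimental day, while the Randomisation procedure section randomises the order.

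The cost is two sentences of analysis wording, plus the normality criterion, settled before analysis. No new data, visits or participants are needed.

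### Does basing the sample size on a DSST standard deviation undermine the power claimed for the SDMT primary endpoint?

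*Combined protocol and SAP*

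**What the plan says.** Under Objectives and endpoints, the single primary endpoint is "Performance on the Symbol Digit Modalities Test (SDMT").

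Under Performance of Cognitive Tests, the battery is RAVLT, Trail Making A and B, SDMT, Letter-Number Sequencing, verbal fluency and RVP, with the DART for verbal IQ. The relevant part reads "Symbol Digit Modalities Test (SDMT) [8] (psychomotor speed and executive function), WAIS-III Letter-Number Sequencing test [9]". DSST is not in the list.

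Under Calculations and statistics, the planning SD comes from "A recent trial applying the cognitive DSST score (part of the above neurocognitive test battery) in type 1 diabetes", with a value "between eu- and hypoglycaemia of 9 [12]". The plan continues: "We suggest a similar level of variance in this study and from previous trial opt to detect differences of 6 or more". It concludes that the 5% level is one "which will allow a sample size of 28 to yield a more than 90% high chance of detecting a true difference in cognition". This is the only place where DSST appears, and the abbreviation is never spelled out. Participant Selection gives the same number, 28, and attributes it to earlier studies as well as to this calculation.

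**The concern.** The SD of 9 and the difference of 6 are the only numerical variance and effect inputs behind the sample size. Neither is labelled as an SDMT value. The paragraph openly carries the SD over from type 1 to type 2 diabetes, but it mentions no change of instrument. By placing the DSST in the battery, it tells the reader that there is none, and the battery list does not bear that out.

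If the source trial used a different test with a different score spread, the power for the SDMT could differ from the figure claimed. The margin above 90% is not wide, so a modest difference in spread would matter. On this view a reader cannot verify the power of the primary comparison, and a null SDMT result would be harder to interpret.

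**Working it through.** **Inputs** (all from Calculations and statistics unless noted)

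- Difference to detect: 6.
- SD: 9, read as the SD of within-participant differences between the two clamp conditions. This reading is inferred.
- Significance level: 5%. Sidedness is not stated; two-sided is assumed.
- n = 28. Each participant has both conditions in a two-period cross-over (Study design), so the comparison is paired.

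**Reproducing the stated figure**

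For a paired t-test the non-centrality parameter is (difference / SD) × √n, on n − 1 degrees of freedom (df).

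- 6 / 9 = 0.667, and √28 = 5.29, so the parameter is 0.667 × 5.29 = 3.53.
- Two-sided 5%, 27 df: power 92.5%.
- With a period term, 26 df: 92.4%.
- One-sided 5%, 27 df: 96.3%.
- The smallest n giving 90% (two-sided, 27 df formula with n − 1) is 26.

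All of these agree with the plan's claim. Treating the conditions as parallel groups gives 42.2% (14 per arm) or 70.3% (28 per arm), so the paired reading is the one that fits.

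**What a different instrument could do**

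The documents give no SDMT SD or SDMT difference. The values below are assumptions on both sides of the planned ones (n = 28, two-sided 5%).

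| SD of differences, difference 6 | Power |
|---|---|
| 7 | 99.2% |
| 8 | 96.9% |
| 9 (plan) | 92.5% |
| 10 | 86.4% |
| 12 | 72.3% |

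| Difference, SD 9 | Power |
|---|---|
| 7 | 97.8% |
| 6 (plan) | 92.5% |
| 5.5 | 87.6% |
| 5 | 80.9% |

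Power is at least 90% when difference / SD is at least 0.636. That means an SD of at most 6 / 0.636 ≈ 9.4 at a difference of 6, or a difference of at least 0.636 × 9 ≈ 5.7 at an SD of 9.

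**Which readings the text allows**

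1. DSST is a slip for SDMT. The SDMT is the only symbol-digit test in the list, and the paragraph says the test is in the battery. The SD of 9 then belongs to the primary endpoint, subject only to the stated assumption of similar variance.
2. A DSST is given but was left off the battery list. The list is then incomplete, and the SD is borrowed from a companion test.
3. The source trial used a test that is not in this battery. The parenthetical is then wrong, and the SD is borrowed from outside the battery.

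The documents do not decide between these. Under each of them, 28 participants are enrolled, the SDMT is primary and the same comparison is made.

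**The case for a change.** The strongest case for a change is that a power claim should be checkable for the endpoint it supports, and this one is not. The threshold is close: an SD about 5% above the assumed value (9.44 against 9) takes power below 90%. The plan does not argue that the SD transfers between tests, and the correction would cost only a sentence or two.

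Part of this stands. The label is inconsistent with the battery list, and the source of the difference of 6 is given only as a previous trial, with no instrument named. The SD is also not stated outright to be that of paired differences. If 9 were a per-condition SD, the SD of differences would be 9 × √(2(1 − ρ)), and power would be 67.2%, 82.0%, 92.5% and 99.2% at assumed correlations ρ of 0, 0.3, 0.5 and 0.7.

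What does not stand is the step from an unclear label to a power claim that fails. Every unfavourable figure above rests on an assumed SD, difference or correlation, and equally plausible values raise the power. A planning SD is an assumption in any case, and this plan already says so for the change of population: "We suggest a similar level of variance in this study".

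Rewriting the power sentence in SDMT terms would not make it better founded. It would fix a sidedness and a paired SD that the plan leaves implicit, and put an SDMT label on numbers with no SDMT source in the documents. Restating it for 28 completers would raise a further question. The analysis rule is "Only data from trial participants who have completed the entire study will be included in the statistical analysis", and no dropout allowance is stated, so that sentence would hold only with no dropout. With 26 completers power is still 90.4%; with 25 it is 89.2%.

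**Conclusion.** The discrepancy between the sample-size paragraph, the battery list and the primary endpoint is real, but it is a matter of labelling and sourcing. The plan's power claim reproduces at 92.5% (92.4% with a period term), given a paired comparison, a two-sided 5% test and 9 as the SD of within-participant differences. No figure in the plan is shown to be wrong, and nothing in the documents puts SDMT power below 90%.

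Following the plan as written yields the same sample size, primary endpoint, design and analysis as a version with the instrument named. The trial's own SDMT data will determine the precision of its result, whichever test supplied the planning SD. No change is called for. When the sample size is reported, the authors can identify the instrument and source of the two inputs.
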